2.2 Study Rationale

One promising strategy to reduce clinical spread is use of antiviral mouth rinses to inactivate SARS-CoV-2 infectability in saliva. Several commercially available mouth rinses have promising *in vitro* data with SARS-CoV-2 and *in vivo* data with other enveloped viruses, with a proposed mechanism of membrane disruption.^{3,11} Ethanol solutions (21% EtOH) have been shown to reduce SARS-CoV-2 viral infectivity levels *in vitro*, and in patients suffering Herpes Simplex Virus-1 flare-ups, a 30 second oral rinse significantly reduced salivary infectivity for over 30 minutes.¹² Cetylpyridinium chloride has promising *in vitro* data for inactivating SARS-CoV-2 infectivity.¹³ Minimal *in vivo* clinical data regarding SARS-CoV-2 exists to-date for most oral rinses.

Despite promising *in vitro* data, there is a dearth of *in vivo* clinical trials interrogating the efficacy of mouth rinses on reducing salivary SARS-CoV-2 viral infectivity. Given the rapid transmission and widespread distribution of the COVID-19 pandemic and its new variants, the development of protocols and treatments mitigating transmission represent a major and urgent unmet public health need; this study will rigorously address the *in vivo* utility of widely available oral rinses in limiting SARS-CoV-2 viral infectivity and their acceptability in the dental healthcare setting.⁵⁻⁸

Like other enveloped viruses, coronaviruses are surrounded by a lipid bilayer which allows for spike glycoproteins required for infection to be inserted.³ The mouth rinses proposed

in this study have shown success in previous studies in disrupting this lipid envelope in other viruses, and there is promise that they will do the same to the SARS-CoV-2 virus. Effect size: Based on our similar viral load studies evaluating mouth rinse efficacy against SARS-CoV-2 and studies about other enveloped viruses, we used power calculations to estimate effect size and determine sample size as a function of length of mouth rinse time course. With simultaneous comparisons across time points (T0-T1, T1-T2, T0-T2, T2-T3, T0-T3, T1-T3), the sample size $n=43$ for each mouth rinse can detect the effect size in Cohen's $d = 0.8$ at 30 minutes, which is between medium and large, under 80% power and 0.016 type-I error rate by Bonferroni correction.¹² To account for 14% of patients having no virus in their saliva and 10% of patient producing insufficient saliva, we plan to enroll 55 participants per arm.

Subjects will be required to rinse their mouths with an unlabeled/blinded mouth rinse for 60 seconds. Per the instructions on the product label, it is recommended to rinse for 30-60 seconds. The longer rinse-time was chosen for this study in order to maximize the antiviral activity of the proposed mouth rinses. The mouth rinses chosen for this study are all commercially available products with known antiviral effects.

The intervention will be administered orally because an oral mouth rinse will be utilized, and the dosage will be 20 mL, dependent on the dosage instructions on the product label. The duration of the intervention will be 60 minutes, with collection of pooled saliva samples pre-rinse and every 15 minutes (0 min, 15 min, 30 min, 45 min, and 60 min) post-rinse. This time period was chosen to be similar to that of a typical dental appointment. Multiple saliva samples will be collected to show how long the proposed mouth rinses are successful in deactivating the virus.

Known and potential risks include breach of confidentiality, slight discomfort, and a low chance of a previously undiagnosed allergy. To minimize risk of breach of confidentiality, all patients will be assigned a unique study ID. There will be no other subject identifiers on samples or data. The linkage file that relates patient's names to study ID numbers will be stored on a UNC secure server. All desktop computers and servers are kept in locked facilities and in accordance with UNC IT/security safeguards and policies. All providers and study researchers have been trained in and abide by HIPAA procedures, and confidential patient information will be stored on secured, encrypted UNC servers. Patients will already have been provided with their COVID status through their healthcare providers, and this confidential medical information will not be released by any study personnel. Some patients may perceive the mouth rinse as causing some discomfort if they dislike the flavor or the bubbling sensation. A small fraction of patients (rare <1%) may be allergic to the mouth rinse. We will ask detailed questions in our screening protocol if patients are allergic to any component of the mouth rinses, but if a patient answers no to all screening questions regarding allergy and then they are allergic, it may lead to an adverse allergic reaction.

The following table lists adverse effects associated with each mouth rinse proposed in this study:

mouth rinse*	Adverse effects
26.9% ethanol plus essential oils	
 • If more than used for rinsing (20ml) is accidentally swallowed, get medical help or contact a Poison Control Center right away. The exact amount used for rinsing (20ml) will be dispensed to study participants, such that they cannot swallow more than 20ml, to reduce the risk of this adverse event. • Poison control: [contact]
0.1% Cetylpyridinium Chloride	
 • If more than used for rinsing (20ml) is accidentally swallowed, get medical help or contact a Poison Control Center right away. The exact amount used for rinsing (20ml) will be dispensed to study participants, such that they cannot swallow more than 20ml, to reduce the risk of this adverse event. • Poison control: [contact]
Sterile water	No contraindications

**All mouth rinses are commercially available in the USA, routinely used in clinical settings, and will be used in an on-label manner.*

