Participants will be asked to give a baseline salivary sample (5ml over 5 minutes) and then asked to rinse with an unlabeled (blinded) antiseptic mouth rinse for 60 seconds according to the table below. The rinses and control will be similar in appearance visually, such that a double-blind can be maintained. The research assistant ([name]) will be the sole unblinded staff member who will perform randomization and communicate the subject's group assignment to blinded study staff, in advance of the visit based on the block randomization schedule. The unblinded staff member will set-up the rinses for the participants appointment minimizing the possibility of study staff being able to identify the blinded rinses. In the instance that [name] is unavailable, [name] or [name] will perform randomization and set-up the rinses. Blind will be strictly maintained except in the case of medical emergency requiring reveal of an individual's rinse identity. The product group key will be provided to the analyzing statistician at the conclusion of the clinical study.

mouth rinse*	Number of participants (sample size)	Group
26.9% ethanol plus essential oils	84	Experimental
0.1% Cetylpyridinium Chloride	84	Experimental
Sterile water	84	Control

**All mouth rinses are commercially available in the USA, routinely used in clinical settings, and will be used in an on-label manner.*

After the participant expectorates the mouth rinse, research staff will collect another salivary sample (T_0 , 2 mL over 5 minutes). During a 10 minute recuperation period, the study participants will answer demographics survey questions and questions regarding the taste, color, flavor and general acceptability of using the mouth rinse as part of routine dental and medical visits as well as in social settings. At 15 minutes post-rinse, the participant will be asked to provide an additional saliva sample (2 mL over 5 minutes), followed by another 10 minute recuperation period. This sequence will be repeated for at

the 30, 45 and 60-minute time points post rinse. At 60 minutes, the study participant will give their final salivary sample (2 mL over 5 min), and study participation will conclude.

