5. STUDY INTERVENTIONS

5.1 Interventions, Administration, and Duration

Patients who meet all inclusion criteria without any exclusions will be asked to give a baseline salivary sample of 5ml over 5 minutes. The patient will then be asked to rinse with an unlabeled/blinded antiseptic mouth rinse for 60 seconds. Once s/he expectorates the mouth rinse, a time 0, 2ml salivary sample will be collected over 5 minutes. Then the patient will have 10 minutes to recuperate, while answering survey questions about their demographics and regarding the taste, color, flavor and acceptability of using the mouth rinse as part of routine dental and medical visits. Intra-oral photographs of notable lesions may be taken to document oral manifestations of COVID-19. At 15 minutes post-rinse, the patient will be asked to provide an additional 2ml saliva samples over 5 minutes,

followed by another 10 minute break. This sequence repeats for the 30, 45 and 60 minute time points. At 60 minutes, the patient will give their last salivary sample, and study participation will conclude. Participants will be provided with a gift card for their participation.

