9. STATISTICAL CONSIDERATIONS

9.1 General Design Issues

A double-blinded, randomized controlled trial was chosen as the study design. It allows us to collect human based data on the effects of commercially available mouth rinses on salivary infectivity and viral load. A crossover study was not pursued because the repeated use of different mouth rinses is likely to confound the results. A 1-hour time-course was chosen to correspond with the average length of most dental procedures. Fifteen minute intervals were chosen to evaluate viral kinetics over time, and to see when infectivity rebounds post- mouth rinse.

Statistical Hypothesis

The central hypothesis of this study is that a 60 second antiseptic mouth rinse will effectively reduce viral infectivity (>50%) of SARS-CoV-2 for a minimum of 30 minutes duration.

The secondary hypothesis is that a 60 second mouth rinse will be well tolerated in a clinical care setting by a majority of patients and providers.

Sample Size Considerations

Based on our similar viral load studies evaluating mouth rinse efficacy against SARS-CoV-2 and other enveloped viruses, we used power calculations to estimate effect size and determine sample size as a function of length of mouth rinse time course.¹² With simultaneous comparisons, the sample size n=43 for each mouth rinse can detect the effect size in Cohen's $d = 0.8$, which is between medium and large, under 80% power and 0.016 type-I error rate by Bonferroni correction.¹² To account for 14% of patients having no virus in their saliva and 10% of patients producing insufficient saliva, we plan to enroll 55 participants per arm.

Statistical analysis of our deidentified data will be performed by [name], the statistician on this project.

Primary Outcomes

The analyses will compare viral RNA level (qRT-PCR) and viral infectivity levels between mouth rinse types and across the time course

Data generated from the qRT-PCR assays will be presented as mean standard deviation for normally distributed data and as median [Interquartile range] for non-normally distributed data. P values will be reported as two tailed. Between group comparisons will be performed using a Student's t test or Mann-Whitney U test. Normality will be assessed using the Kolmogorov-Smirnov test, and logistic regression will be performed with robust standard errors.

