The viral infectivity analysis will compare infectivity levels between mouth rinse types and across the time course for calculation of the reduction factor (RF). The RF will be calculated as the difference in the quotient of the infection titre before ('control titration') and after the mouth rinse ('remaining virus'). Therefore, the log₁₀ titre and its (double) standard deviation (SD) were calculated as well as the variance of the RF.

Secondary Outcomes

Survey statistical analysis will be conducted by Odum Institute's statistical consultant, [name]. We will use descriptive statistics, frequency counts and means to evaluate feasibility and acceptability of using point-of-care mouth rinses in clinical workflow.

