9.2 Sample Size and Randomization

Based on similar viral infectivity studies evaluating antiviral mouth rinse efficacy, we were able to run power calculations to estimate effect size and determine sample size as a function of length of mouth rinse time course. The sample size is justified by a paired t-test on outcomes between time points. With simultaneous comparisons, the sample size n=43 for each mouth rinse can detect the effect size in Cohen's $d = 0.8$ at 30 minutes, which is between medium and large, under 80% power and 0.016 type-I error rate by Bonferroni correction.¹² To account for 14% of patients having no virus in their saliva and 10% of patients producing insufficient saliva, we plan to enroll 55 participants per arm.

The statistical consultant on this project will create a block randomization tool for the study staff; the unblinded staff member will randomize a participant once enrollment compliance has been confirmed and consent has been given. The participant's group assignment will then be communicated to the blinded study staff. IRB approved study personnel will ask participants screening questions to confirm eligibility for enrollment. After consent and screening, the randomization tool will be used by study staff to assign the subject to a study group.

The researcher responsible for collecting the salivary samples will be blinded to the mouthwash solution, as they will be given a pre-aliquoted mouth rinse in an unlabeled tube to provide to the patient for the rinse.

The PI, Co-I, study coordinators and study personnel who work for GoHealth are authorized to break the blinding based on emergency medical necessity such as if a patient suffers an allergic or adverse reaction to one of the mouth rinses. Though highly unlikely as all mouth rinses are sold commercially at Walgreens and CVS, adverse or allergic reactions are possible. Using the numerical code associated with the participant and mouth rinse syringe, the study personnel responding to the emergency can reference the block randomization schedule to determine the mouth rinse type, to inform the emergency medical workers, poison control or the emergency room what type of mouth rinse product led to the reaction.

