Power Calculation: Based on our similar viral load studies evaluating mouth rinse efficacy against SARS-COV-2 and other enveloped viruses, we used power calculations to estimate effect size and determine sample size as a function of length of mouth rinse time course.¹² The sample size is justified by a paired t-test on outcomes between time points. With simultaneous comparisons, the sample size n=43 for each mouth rinse can detect the effect size in Cohen's d =0.8, which is between medium and large, under 80% power and 0.016 type-I error rate by Bonferroni correction.¹² To account for 14% of patients having no virus in their saliva, we plan to enroll 55 participants per arm. Analyses will compare viral RNA level (qRT-PCR) and viral infectivity levels between mouth rinse types and across the time course. ANCOVA models will be utilized to look at changes in viral load and infectivity logarithmically before and after treatment.

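### Section 2.2 lists six time pairs beside a Bonferroni alpha of 0.016 that fits three at a family-wise 0.05, its T0 label is unclear, and the comparisons with water have no stated alpha or deciding contrast

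*Combined protocol and SAP*

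**What the plan says.** **Alpha and pair list.** The effect-size text in section 2.2 sets out six comparisons, "With simultaneous comparisons across time points (T0-T1, T1-T2, T0-T2, T2-T3, T0-T3, T1-T3", and gives n=43 per rinse "under 80% power and 0.016 type-I error rate by Bonferroni correction". Sections 9.1, 9.2 and 9.5 repeat 0.016 for simultaneous comparisons without a count. No section states a family-wise alpha.

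**Test behind the sample size.** Sections 9.2 and 9.5 say: "The sample size is justified by a paired t-test on outcomes between time points". Section 9.2 adds that "the sample size n=43 for each mouth rinse can detect the effect size in Cohen's $d = 0.8$ at 30 minutes".

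**Time labels.** Section 3 has staff collect, after the rinse is expectorated, "another salivary sample (T_0 , 2 mL over 5 minutes". Section 5.1 likewise says that "a time 0, 2ml salivary sample will be collected over 5 minutes" once the rinse is spat out. T1, T2 and T3 are not defined.

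**Comparisons between rinses.** Section 9.1 says: "The analyses will compare viral RNA level (qRT-PCR) and viral infectivity levels between mouth rinse types and across the time course". For infectivity it says: "The viral infectivity analysis will compare infectivity levels between mouth rinse types and across the time course for calculation of the reduction factor (RF". For RNA, sections 9.1 and 9.5 name a t test or Mann-Whitney test with a Kolmogorov-Smirnov normality check. The last sentence of section 9.5 also names ANCOVA for both outcomes on the log scale.

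**The concern.** A Bonferroni alpha is the family-wise alpha divided by the number of tests. Here the divisor implied by 0.016 and the number of listed tests disagree within one sentence, unless the family-wise alpha is something other than the usual 0.05. The labels make it harder to tell which three or six tests were meant, and whether any of them measures a fall from the pre-rinse sample.

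The second part concerns the control arm. A fall within one rinse group cannot separate an antiseptic effect from the effect of rinsing with water or of repeated sampling. The randomised comparison with water can, yet the plan does not say which contrast, at what alpha and at which time, shows that a rinse beats water. Section 9.4 leaves the conclusion on which rinse is more effective to an unmasked study committee, so that rule should be on paper before the assay results exist.

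**Working it through.** **1. Inputs.** From section 2.2: six pairs (all pairs of four times, 4 x 3 / 2 = 6), alpha 0.016, power 80%, d = 0.8, n = 43. From section 9.1: two-tailed P values. Assumed: family-wise alpha 0.05.

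**2. The plan's own figures.**
- 0.05/3 = 0.01667, which truncates to 0.016; 0.05/6 = 0.00833.
- Sums: 3 x 0.016 = 0.048; 6 x 0.016 = 0.096.
- A two-sided paired t-test at 0.016 with d = 0.8 on the SD of differences reaches 80% power at n = 20, so 43 is not reproduced. That is a separate question. Here it matters only that 43 exceeds the need.

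**3. Family-wise error if the listed pairs are run as paired t-tests.** Simulated with no effect, n = 43, four times, 200,000 runs per setting. The three columns are compound symmetry, AR(1) with 0.5 and AR(1) with 0.8.

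| Tests | CS | AR 0.5 | AR 0.8 |
|---|---|---|---|
| six pairs at 0.016 | 7.6% | 7.4% | 7.1% |
| three pairs at 0.016 | 4.3% | 4.2% | 4.1% |
| six pairs at 0.0083 | 4.3% | 4.1% | 3.9% |

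**4. The two readings of T0** (T1 to T3 assumed to follow at the next sampling times).
- T0 is the immediate post-rinse sample, as in sections 3 and 5.1. Then T1, T2, T3 are 15, 30 and 45 minutes. Three pairs (T0-T1, T1-T2, T0-T2) lie within 30 minutes and 0.05/3 would suit those three. But six are listed, and none contains the pre-rinse sample.
- T0 is the pre-rinse sample. Then T3 is 30 minutes, which agrees with the power statement at 30 minutes. But all six pairs lie within 30 minutes, 0.05/3 does not suit them, and the label contradicts sections 3 and 5.1.

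**5. Does the corrected alpha threaten n = 43?** Paired power at 0.00833:
- d on the SD of differences: 99%.
- d on the raw SD, effective size 0.8 / sqrt(2(1 - r)): 82% at correlation r = 0 and 93% at r = 0.25.

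The plan does not say which SD scales d. For any correlation of zero or above, n = 43 keeps at least 80%.

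**6. Cost of a rule for the comparisons with water.** Two-sample t-test, before any baseline adjustment. The plan gives no between-arm effect size, so d is assumed. The 72 is 84 x 0.86, the enrolment in section 3 less the 14% expected to have no virus.

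| n per arm, d | at 0.05 | at 0.025 |
|---|---|---|
| 43, 0.8 | 96% | 92% |
| 43, 0.5 | 63% | 52% |
| 72, 0.5 | 85% | 77% |

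**7. Gain from baseline adjustment.** With pre/post correlation r (assumed 0.5 and 0.7), ANCOVA saves r² of the variance compared with an unadjusted test of levels: 25% and 49%. Compared with a test of changes it saves 1 - (1 + r)/2: 25% and 15%.

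**The case against.** **The alpha may not be wrong.** With a family-wise alpha of 0.10, 0.10/6 = 0.0167 fits six pairs. Three tests could also stand for the three pairwise contrasts among three rinses, and section 9.1 gives 0.016 without naming time pairs. Neither reading is stated, however, and sections 9.2 and 9.5 tie the calculation to paired tests between times. The sentence still needs correcting or explaining.

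**The label affects only the power list.** This stands. A reader might infer that the analysis ignores the pre-rinse sample. It does not: the reduction factor compares titre before and after the rinse, and the ANCOVA looks at change from before to after.

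**Thirty minutes is already the plan's time.** This largely stands. It appears in the hypotheses (sections 1.1, 9.1 and 9.4.1) and in the power text (sections 2.2 and 9.2). It is not carried into the text on comparisons between rinses.

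**A large false-positive risk.** A reader might infer that the comparisons with water carry a false-positive chance of 18% to 35%. That is the simulated figure for ten tests (two antiseptics, five post-rinse times) at 0.05 each, with any one positive counting as success and between-time correlation from 0.9 to 0.3. No section states that alpha or that rule. The stated hypothesis is nearer to a joint one, a reduction that persists to 30 minutes. If significance in the same direction is required at 0, 15 and 30 minutes for either antiseptic, the figure is 0.1% to 4.1%. The plan fixes neither rule, so neither range is its error rate.

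**Choice after the results.** A reader might infer that the unmasked committee will pick the winning comparison. The documents do not show this: the statistician analyses first, receives the product key only at the end of the clinical study, and laboratory samples are coded. The plan simply does not rule it out.

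**Two RNA methods.** Group tests and ANCOVA can coexist, so this is no contradiction. What is missing is which one decides.

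**Conclusion.** The pair list, alpha and T0 label in section 2.2 are wrong as written, in the sense that they cannot all stand together under a family-wise alpha of 0.05. That alpha is an assumption. If the six paired tests were run at 0.016, family-wise error would be about 7% to 8% per arm instead of at most 5%. A reader might infer that the trial is therefore too small; the documents do not support that, because n = 43 keeps 82% to 99% paired power at 0.0083 (correlation zero or above).

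The missing alpha and deciding contrast for the comparisons with water are a gap in specification that is cheap to close, not a demonstrated error rate. Both parts should be fixed; neither shows that the trial cannot answer its question.

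**What to change.** 1. **Labels, list and alpha.** Give the pre-rinse sample its own label and define every other time label. State the family-wise alpha. Make list and alpha agree in sections 2.2, 9.1, 9.2 and 9.5: either 0.0083 for six pairs, or three named pairs, including pre-rinse versus 30 minutes, at 0.05/3.

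2. **Deciding comparison for infectivity.** Make the ANCOVA of section 9.5 on log10 infectivity, adjusted for the pre-rinse value, the deciding analysis at 30 minutes. Test each antiseptic versus water at two-sided 0.025, or by Holm. State how zero or below-limit titres enter the log scale, since 14% of patients are expected to have no virus and large reductions are hypothesised. Keep ethanol versus CPC as a pre-specified comparison, for example tested after the contrasts with water, because finding the most effective rinse is a stated aim (sections 3 and 9.4).

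3. **Size of effect.** Report the percent reduction with its confidence interval against one reconciled threshold. Sections 1.1 and 9.4.1 say more than 95% (20-fold, 1.30 log10) and section 9.1 says more than 50% (2-fold, 0.30 log10). A significant difference from water shows neither by itself.

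4. **RNA.** Use the same baseline-adjusted model, with a rank-based sensitivity analysis for non-normal data.

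**Cost.** Wording only, with no extra participants or samples. Power per contrast is somewhat lower at 0.025 than at 0.05: 92% versus 96% at n = 43 and an assumed d of 0.8, before baseline adjustment, which recovers part of it. Isolated differences at other times become supportive. The assays are run weeks to months after sampling, so the wording should be settled before results are available.

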1. STUDY OBJECTIVES

1.1 Primary Objective

The primary objective of this study is to determine the efficacy of antiseptic mouthwashes on reducing SARS-CoV-2 cellular infectivity in COVID+ patient saliva. *We hypothesize that COVID-19+ patients will have a >95% reduction in SARS-CoV-2 viral infectivity following a 60 second oral rinse with an antiseptic mouth rinse and that this reduction will persist for at least 30 minutes.* This primary objective will focus on quantifying SARS-CoV-2 viral infectivity and RNA level using an *in vitro* infectivity assay and quantitative real time PCR. This objective provides urgently needed data to guide healthcare workers on the proper use of specific commercially available mouthwashes capable of reducing SARS-CoV-2 viral infectivity and potentially limiting COVID-19+ transmission.

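### The stated 80% power is not the chance of confirming the hypothesised >95% (or >50%) reduction, and no planned analysis tests either threshold

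*Combined protocol and SAP*

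**What the plan says.** Section 1.1 hypothesises that patients "will have a >95% reduction in SARS-CoV-2 viral infectivity following a 60 second oral rinse with an antiseptic mouth rinse" and that this lasts at least 30 minutes. Section 9.4.1 repeats it. The Statistical Hypothesis paragraph of section 9.1 has a lower bar: a rinse will "effectively reduce viral infectivity (>50%) of SARS-CoV-2 for a minimum of 30 minutes duration".

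One power statement appears, with small variations, in sections 2.2, 9.1 and 9.2 and in the Power Calculation paragraph of section 9.5: 43 per rinse, Cohen's d of 0.8, "which is between medium and large, under 80% power and 0.016 type-I error rate by Bonferroni correction". The test is named in sections 9.2 and 9.5 only: "The sample size is justified by a paired t-test on outcomes between time points". Section 2.2 lists the simultaneous comparisons as "T0-T1, T1-T2, T0-T2, T2-T3, T0-T3, T1-T3".

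No section gives an SD, the scale of d, or the percent or log10 reduction that d=0.8 represents. The planned analyses (sections 9.1 and 9.5) are t or Mann-Whitney tests between groups, logistic regression, a reduction factor with its variance, and ANCOVA on the log scale. None compares the reduction with 95% or 50%.

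**The concern.** A claim that the reduction exceeds a margin needs evidence that excludes the margin, for example a lower confidence limit above it. A paired t-test named without a margin has, on its ordinary reading, a null of zero mean change. Rejecting that null shows some reduction. It does not show one above 95%, or above 50%.

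Section 1.1 says the results should guide healthcare workers on the use of specific mouthwashes. A reader who sees 80% power beside a >95% hypothesis will take it as the chance of confirming that hypothesis. A significant before-after change could then be reported as confirmation although the data are compatible with a much smaller reduction.

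**Working it through.** **Inputs from the documents.** n=43 per rinse, d=0.8, alpha 0.016 and 80% power (sections 2.2, 9.1, 9.2, 9.5); paired t-test (sections 9.2, 9.5); thresholds 95% (sections 1.1, 9.4.1) and 50% (section 9.1). Two-sided testing is taken from "P values will be reported as two tailed" in section 9.1, which is written for the qRT-PCR data.

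**Assumptions.** The null of the paired t-test is zero. For the conversions below, d is on the scale of the log10 change from the pre-rinse sample, changes are normal, and a single time point is tested. The SD of the change is not given and is set at 0.5, 1.0, 1.5 and 2.0 log10.

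**Step 1: the plan's own figure.** Power of a two-sided paired t-test is P(T > t_crit), where T is noncentral t with n−1 df and noncentrality d√n. For n=43, t_crit(0.992; 42 df) = 2.510 and 0.8 × √43 = 5.25, so power is 99.6%. With n=20 it is 81%. The 80% is not reproduced by the named test with the stated inputs, so what it refers to is unknown.

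**Step 2: thresholds on the log10 scale.** −log10(0.05) = 1.301 and −log10(0.50) = 0.301.

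**Step 3: what d=0.8 would mean.** The reduction is 1 − 10^(−0.8 × SD). It equals 95% when SD = 1.301/0.8 = 1.63, and 50% when SD = 0.301/0.8 = 0.38.

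| Assumed SD (log10) | 0.5 | 1.0 | 1.5 | 2.0 |
|---|---|---|---|---|
| Reduction at d=0.8 | 60.2% | 84.2% | 93.7% | 97.5% |

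**Step 4: power for the threshold claims.** The null is the threshold and the upper tail is 0.008. The noncentrality is (L − threshold)/SD × √43, where L = −log10(1 − true reduction). Example: true 97%, SD 1.0. L = 1.523, (1.523 − 1.301)/1.0 × 6.557 = 1.455, and P(T > 2.510) = 15.8%.

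| Claim; true reduction (n=43) | SD 0.5 | SD 1.0 | SD 1.5 | SD 2.0 |
|---|---|---|---|---|
| >95%; 95% | 0.8% | 0.8% | 0.8% | 0.8% |
| >95%; 97% | 65.5% | 15.8% | 7.0% | 4.4% |
| >95%; 99% | 100% | 97.8% | 70.6% | 42.2% |
| >50%; 95% | 100% | 100% | 96.5% | 77.5% |
| Any change from zero; 95% | 100% | 100% | 99.9% | 95.6% |

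The first and last rows have the same truth, a 95% reduction. Only the null differs.

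**Step 5: the larger enrolment figure.** The Précis and section 3 give 84 per arm, not 55. With the stated losses, 84 × 0.86 × 0.90 = 65 evaluable. Power to show >95% at a true 97% is then 86%, 25%, 11% and 6%.

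**The case against.** The strongest reply is that the >95% sentence states an expected effect, not a margin to be proven. Sizing a trial to detect less than one expects is conservative. That stands in part. A reader might infer that d=0.8 contradicts the hypothesis because it can be less than a 95% reduction, and the documents do not support that. With no SD given, d=0.8 may lie on either side of 95%: it is below at SDs under 1.63 and above at 2.0. A smaller detectable effect is in any case no contradiction. But the sentence is worded as the hypothesis in both the objective and the primary outcome, and nothing in the plan calls it descriptive.

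Second, under the >50% hypothesis of section 9.1 the picture is much better: d=0.8 exceeds 50% at all four SDs, and power is ample if the truth is near 95%. That also stands. Even so, no test against 50% is planned. If the truth is only d=0.8, power to show >50% is 12%, 77%, 92% and 96% across the four SDs, so the stated 80% does not describe that claim either.

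Third, the conversion of d rests on an unstated scale and baseline. This is correct. Section 3 labels T0 as the sample taken after expectoration; on that labelling the pairs listed in section 2.2 contain no pre-rinse sample, and d=0.8 would not be a reduction caused by the rinse.

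Finally, a reader might infer that the 80% is simply power against zero change at d=0.8. Step 1 shows that it is not: that power is 99.6%.

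**Conclusion.** The point holds in this form: the hypothesis is a margin claim, the stated power carries no margin, and no planned analysis tests one. This does not depend on the SD, on the value of n, or on which threshold governs. It does depend on reading the paired t-test as a test against zero, which the documents imply but do not write out.

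The size does depend on assumptions. For a >95% claim with n=43, power runs from 0.8% at a true 95%, through 4% to 66% at a true 97%, to 42% to 100% at a true 99%, over SDs of 2.0 down to 0.5. For a >50% claim at a true 95% it is about 78% to 100%. These figures are for one time point. They do not cover persistence to 30 minutes, or post-rinse samples with no plaques, which have no log10 titre. The documents do not support saying that the trial is too small; they support saying that its power for its own claim is unstated.

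**What to change.** 1. Reconcile the 95% threshold (sections 1.1 and 9.4.1) with the 50% threshold (section 9.1).
2. In sections 9.1 and 9.5, choose one of two rules. Either conclude that the threshold is met only if the lower confidence limit of the log10 reduction from the pre-rinse sample exceeds it at each time point through 30 minutes; or make the primary claim a greater reduction than with water, report the percent reduction with its confidence interval, and keep the threshold as a descriptive target.
3. In sections 2.2, 9.1, 9.2 and 9.5, do not present the 80% as power for the threshold claim. Do not relabel it as power against zero change either, since the stated inputs give 99.6% for that test. Recompute the figure for the chosen claim with the SD from the sponsor's prior study, and state the scale and baseline to which d refers.

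The cost is protocol and SAP wording plus one short calculation. Enrolment does not change. The downside is that the stated power for a >95% claim may become less favourable.
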